# **6.2.** Follow Up Assessments

All participants will be assessed for physical examination findings and vital signs following signing of the informed consent form (ICF) and for AEs and SAEs, throughout the study for each treatment group.

Serum samples will be collected from all participants to test for the presence of anti-IL-10 antibodies and IL-10 protein. Samples will be analyzed using a validated assay by an independent, central bioanalytical laboratory. Procedures for collection, storage, and shipping of immunogenicity samples are described in the study Lab Manual.

Whole blood samples will be collected from all participants to test for the presence of XT-150 plasmid. Samples will be analyzed using a validated assay by an independent, central bioanalytical laboratory. Procedures for collection, storage, and shipping of immunogenicity samples are described in the study Lab Manual.

Efficacy assessments will be performed at Baseline, on Day 7, Day 14, Day 30, and approximately monthly thereafter for up to 9 months. Efficacy endpoints will be evaluated at each study visit and overall.

A telephone call documenting safety and efficacy assessments may be used for participants unable to physically attend follow up visits due to COVID-19 infection or SARS-CoV-2 exposure concerns. Home services may be employed for blood collections.

## **6.3.** Number of Participants

Up to 72 participants will receive study drug administration and evaluated.

## 6.4. Expected Duration of Subject Participation

Subject participation will require a commitment of approximately 9 months of safety, tolerability, and efficacy evaluation. In addition, a screening visit will occur up to 30 days before enrollment.

Baseline assessments for study eligibility will be completed within one day before study drug administration. Day 0 is defined as the day of study drug administration. Subsequent study days are defined by the number of consecutive calendar days thereafter.

Follow-up visits will occur on Study Day 7, Study Day 14, Study Day 30, and approximately monthly thereafter.

# 6.5. Method of Treatment Assignment and Blinding

After informed consent has been obtained, participants will be screened for study eligibility before enrollment.

Participants will be randomly enrolled into one of 3 groups, two XT-150 treatment groups (150 μg or 450 μg) or placebo.

Instructions for study drug preparation and dosing are given in Section 8.

# 7. SELECTION, DISCONTINUATION, AND WITHDRAWAL OF SUBJECTS

To be enrolled in this study, all participants must meet all of the following inclusion criteria and none of the exclusion criteria.

## 7.1. Participant Inclusion Criteria

Participants are required to meet ALL of the following inclusion criteria:

- 1. Male or female, between 18 and 90 years of age, inclusive.
- 2. Sufficiently severe facet arthropathy of lumbar facets as determined by imaging (e.g., MRI, CT, X-Ray, etc.) to establish an underlying basis of disease, as determined by usual bony and ligamentous signs of osteoarthritis (OA). Use of historical images permitted if obtained within the last 12 months.
- 3. Complaint of nociceptive, mechanical pain of lumbar spine, in particular pain localized to paramedian axis as opposed to midline or radicular. Radicular pain as a secondary finding may be allowed if it is in addition to mechanical pain and can be clinically distinguished by subject
- 4. LBP (Low Back Pain) worsened by activity or motion of region
- 5. Have had a positive diagnostic facet pain block with lidocaine; admittance if subject gains 50% relief of pain within 30 minutes of test injection
- 6. Be free of local or intra-articular infection, tumor or other causes of localized LBP, for example, spondylolysis/pars defect, and adjacent vertebral body compression fracture based on imaging evaluation.
- 7. Symptomatic disease because of osteoarthritis, established by imaging of facet joint and defined as a worst pain of at least 50 at the Screening Visit and the Baseline (Day 0) Visit (based on scale of 0 to 100, with 100 representing "pain as bad as you can imagine") using Visual Analog Scale (VAS).
- 8. Stable analgesic regimen during the 4 weeks prior to enrollment. Participants who are not currently on any analgesics at the time of enrollment because they have discontinued prior analgesic therapy due to intolerance or lack of effect may be included. New analgesics or changes to the pre-established regimen during the study, with the exception of rescue medication use, are not permitted.
- 9. Inadequate pain relief with prior therapies lasting  $\geq 3$  months.
- 10. In the judgment of the Investigator, acceptable general medical condition
- 11. Heterosexually active participants, male and female who are not surgically sterile or postmenopausal, must agree to use effective contraception, including abstinence, for the duration of the study and for 3 months after the study is completed
- 12. Have suitable facet joint anatomy for intra-articular injection
- 13. Willing and able to return for the follow-up (FU) visits

14. Able to read and understand study instructions, and willing and able to comply with all study procedures

## 7.2. Subject Exclusion Criteria

Participants must NOT meet any of the following exclusion criteria:

- 1. Hypersensitivity, allergy, or significant reaction to lidocaine or any ingredient of the study drug, including double-stranded DNA,
- 2. Facet injection with glucocorticoid/corticosteroid in the past 6 months
- 3. Lumbar medial branch nerve ablation (e.g., by radiofrequency technique) within the past 12 months
- 4. Prior lumbar fusion surgery
- 5. Prior or existing medial branch nerve stimulation device (e.g. Mainstay device)
- 6. Scheduled surgical procedure or nerve ablation to joint within the next 6 months; participant agrees not to schedule a surgical procedure, nerve ablation, or added facet injection within 6 months of study treatment
- 7. High peri-operative risks which in the judgment of the investigator preclude a safe facet joint injection procedure (e.g. extreme obesity putting injection accuracy at risk, etc.)
- 8. Current treatment with immunosuppressive (systemic corticosteroid therapy [equivalent to >10mg/day prednisone] or other strong immunosuppressant)
- 9. History of immunosuppressive therapy; high-potency systemic steroids in the last 3 months.
- 10. Currently receiving systemic chemotherapy or radiation therapy for malignancy
- 11. Clinically significant hepatic disease as indicated by clinical laboratory results ≥3 times the upper limit of normal for any liver function test (e.g., aspartate aminotransferase, alanine aminotransferase, lactate dehydrogenase)
- 12. Severe anemia (Grade 3; hemoglobin <8.0 g/dL, <4.9 mmol/L, <80 g/L; transfusion indicated), Grade 1 white cell counts (lymphocytes <LLN 800/mm3; <LLN 0.8 x 109 /L, neutrophils <LLN 1500/mm3; <LLN 1.5 x 109 /L)
- 13. Positive serology with reflex for human immunodeficiency virus, hepatitis B virus, or hepatitis C virus within 4 weeks of commencing the study
- 14. Significant neuropsychiatric conditions, dementia, major depression, or altered mental state that in the opinion of the Investigator will interfere with study participation
- 15. Current treatment with systemic antibiotics or antivirals (EXCEPTION: topical treatments)
- 16. Current treatment with anticoagulants, other than low-dose aspirin. Patients, if medically feasible, can interrupt anticoagulant therapy by following local medical practice protocol for intra-articular injections for patients on anticoagulant, antiplatelet therapy.

- 17. Known or suspected history of active alcohol or intravenous/oral drug abuse within 1 year before the screening visit
- 18. Use of any investigational drug or device within 1 month before enrollment or current participation in a trial that included intervention with a drug or device; or currently participating in an investigational drug or device study.
- 19. Any condition that, in the opinion of the Principal Investigator (PI), could compromise the safety of the participant, the participant's ability to communicate with the study staff, or the quality of the data

# 7.3. Requalification for Entry

Participants not fulfilling the entry criteria and not treated may be rescreened for participation if their eligibility characteristics have changed. The screening lidocaine facet injection procedure may be repeated one time to identify the joint that is causing pain.

## 7.4. Participant Withdrawal Criteria

## 7.4.1. Withdrawal from Study Protocol

Participants who wish to withdraw completely from this clinical study should be encouraged to complete the assessments for Day 270/Termination. However, participants may withdraw consent to participate in this study at any time without penalty or loss of benefits to which the participant is otherwise entitled. Every reasonable effort should be made to determine the reason a participant withdraws prematurely, and this information should be recorded on the appropriate page(s) of the case report form (CRF). Participants may be withdrawn from the study for any of the following reasons:

- Participant unable or unwilling to continue
- Participant's perceived lack of benefit
- Participant elects to withdraw informed consent
- Due to an adverse event
- Protocol non-compliance
- Participant is lost to follow up
- The PI considers that it is in the participant's best interest not to continue participation in the study

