## 7.4.2. Early Discontinuation from Study Drug Administration

If a participant needs to discontinue study drug, the reason (i.e. due to an SAE, need for an excluded medication, etc.) should be documented in the eCRF.

NOTE: The Medical Monitor should be contacted to discuss whether to continue with planned XT-150 dosing in the event that the participant situation changes significantly in the 24 hours prior to XT-150 injection such that participant safety is at risk.

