#### **8.5.1.** Prohibited Medications

See exclusion criteria (Section 7.2).

The following treatments are prohibited prior to study drug administration at Day 0 and Day 90:

- Current treatment with antibiotics or antiviral agents (exception: topical treatments)
- Current treatment with immunosuppressive agents
- Current use of systemic steroids (equivalent to >10 mg/day prednisone)
- Current treatment with anticoagulants, other than low-dose aspirin. Patients, if medically feasible, can interrupt anticoagulant therapy by following local medical practice protocol for intra-articular injections for patients on anticoagulant, antiplatelet therapy.

Concomitant medications for pain will be allowed at doses and frequencies prescribed prior to the study treatment. In the event a participant requires additional analgesic treatment during study participation, he/she should take the protocol-specified rescue medication. Introduction of new medications to treat FJOA pain during the study period is prohibited and considered a protocol deviation.

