### 7.3. Handling of Missing Data

- Unless otherwise specified, missing values for individual data points will remain as missing. Missing values will not be imputed and only observed values will be used in data analyses and presentations.
- For efficacy analyses, examining the number of participants with 30%, 50%, or 75% improvement in VAS, participants with missing data will be included in the analysis as participants who have not met the criteria for improvement.
- In all other cases, where individual data points are missing, categorical data will be summarized based on reduced denominators (ie, only participants with available data will be included in the denominators).
- Any partial dates will be presented using the CDISC standard ISO.8601 date format as shown in the SDTMIG v3.3 Section 4.4.2.

- All AEs with partial or missing dates and times will be considered treatmentemergent unless a partial start date indicates the AE began before the start of study medication or a stop date indicates the AE ended before the start of study medication.
  - For determination of treatment emergent AEs with partial start dates using the definition above, if the non-missing portion of the partial date is the same as the start of treatment or after (ex: same or later month and year), then it will be considered treatment emergent.

Ex: If treatment begins March 12th, 2022 and an AE has a partial start date of March 2022 (missing day), it will be considered treatment emergent.

- All medications with partial or missing dates recorded on the concomitant medication eCRF will be considered concomitant unless a partial stop date clearly indicates it was stopped before the first dose of study treatment.
  - For determination of concomitant medications with partial stop dates using the definition above, if the missing part of the partial date is the same (same month or year) as the start of treatment or earlier, then it will be considered treatment emergent.

Ex: If treatment begins March 12th, 2022 and a medication has a partial stop date of March 2022 (missing day), it will be considered concomitant.

	-
	-
	_

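### Protocol 7.4.1 permits withdrawal from the whole study for lack of benefit, an adverse event or non-compliance, and 7.4.2 does not say that visits continue, so Day 270 VAS and later AE data can be lost for outcome-related reasons

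*Protocol*

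**What the plan says.** **Leaving the study (Protocol 7.4.1).** "Participants may be withdrawn from the study for any of the following reasons" introduces seven entries, among them "Participant's perceived lack of benefit", "Due to an adverse event" and "Protocol non-compliance". The same section says "Participants who wish to withdraw completely from this clinical study should be encouraged to complete the assessments for Day 270/Termination".

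**Stopping study drug (Protocol 7.4.2).** "If a participant needs to discontinue study drug, the reason (i.e. due to an SAE, need for an excluded medication, etc.) should be documented". The section is silent on whether visits go on afterwards.

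**New pain treatment (Protocol 8.5.1).** "Introduction of new medications to treat FJOA pain during the study period is prohibited and considered a protocol deviation".

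**Contact efforts (Protocol synopsis, Duration of Treatment).** For participants who miss follow-up, the site makes repeated attempts, by telephone or registered letter, to find the reason and obtain the termination assessments.

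**Replacement (Protocol 7.5).** None after randomization.

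**Missing data (SAP 7.3).** The default, which other text may override, is "Missing values will not be imputed and only observed values will be used in data analyses and presentations". The 30%, 50% and 75% VAS improvement analyses instead count missing as not improved.

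**Visit windows (SAP 7.5, Table 4).** An end-of-study assessment goes to the analysis visit in which it falls. The Day 270 window opens at Day 253.

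**The concern.** Treatment is two injections, on Day 0 and Day 90, and the primary efficacy endpoint is the change in VAS at Day 270. In the last 180 days there is no dose left to stop, so taking someone out of the study then does nothing except end data collection.

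Lack of benefit should be reported more often where treatment does not work, and adverse events more often where it causes them. If either leads to withdrawal from the study, the participants with a Day 270 VAS are a selected group, and the selection can differ between arms. The link for non-compliance is weaker.

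Safety, the primary objective, is also touched. Protocol 10.2 collects AEs through the last visit. After discharge, Protocol 10.6 follows only unresolved SAEs. A participant withdrawn for a non-serious AE has no stated follow-up of that event, and the antibody samples at Days 180 and 270 (Protocol 12) may not be drawn.

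**Working it through.** **1. The plan's own figure.** The documents give no dropout rate, SD or effect size for VAS. The only precision figure is in Protocol 14.1: at a 50% responder rate, a 95% interval of about 29% to 71%. The exact (Clopper-Pearson) interval for 12 of 24 is 29.1% to 70.9%, so it reproduces and confirms 24 per arm as the base.

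**2. Do the safeguards yield a Day 270 value?**
- The encouragement in 7.4.1 is not a requirement. It addresses participants who themselves want to leave, not those withdrawn by the site.
- The contact efforts in the synopsis aim at a termination assessment, not at continued visits.
- A termination visit at Day 150, for example, falls in the SAP window for Day 150 (136 to 165). Only an assessment on Day 253 or later counts as Day 270.

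So neither safeguard provides the endpoint for someone who leaves before Day 253.

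**3. Size in an observed-case comparison (assumed inputs).** Let *m* be the proportion of an arm withdrawn and *g* the mean VAS change in leavers minus that in stayers, equal in both arms. The full-arm mean is the observed mean plus *m* × *g*. For active minus placebo:

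observed − full = (*m*_placebo − *m*_active) × *g*

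- Example: (0.25 − 0.10) × 20 = 3.0 points on the 0–100 scale. With 24 per arm, 25% is 6 participants and 10% is 2.4.
- Low end: 0.05 × 10 = 0.5 points.
- High end: 0.20 × 30 = 6.0 points.
- Equal loss in both arms with an equal gap: (0.20 − 0.20) × 20 = 0.

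A difference of 5 to 20 percentage points is 1.2 to 4.8 participants out of 24.

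**4. Check with an explicit mechanism (assumed inputs).** Normal VAS change, SD 25, placebo mean −15; anyone with no improvement (change above 0) is withdrawn with probability *q*; observed values only; 1,000,000 simulated per arm.

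| True difference | *q* | Missing, placebo / active | Observed difference | Shrinkage |
|---|---|---|---|---|
| −10 | 0.25 | 6.9% / 3.9% | −9.29 | 0.71 |
| −10 | 0.50 | 13.7% / 7.9% | −8.43 | 1.57 |
| −10 | 0.75 | 20.5% / 11.9% | −7.26 | 2.74 |
| −15 | 0.25 | 6.9% / 2.9% | −14.00 | 1.00 |
| −15 | 0.50 | 13.7% / 5.8% | −12.73 | 2.27 |
| −15 | 0.75 | 20.6% / 8.6% | −11.10 | 3.90 |

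The shrinkage of 0.7 to 3.9 points (about 7% to 27% of the true difference) lies inside the range in step 3.

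**5. Set against precision.** With an assumed SD of 25, the 95% half-width for a two-arm difference is 1.96 × 25 × √(2/*n*): 14.15 points at *n* = 24, 14.77 at 22, 15.90 at 19 and 16.81 at 17 (about 10%, 20% and 30% loss).

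**6. Direction.** Lack-of-benefit withdrawal that is commoner on placebo pulls the difference toward zero. If adverse events remove more poor outcomes on active, the sign in step 3 reverses. The two can offset.

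**The case against.** **The list is permissive.** It says participants may be withdrawn. A reader might infer that Day 270 pain is bound to be lost, but the text supports only that it can be. Several entries are the participant's own choice, which no wording can prevent. This stands.

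**A deviation need not end participation.** A reader might infer that someone who starts a new analgesic will be withdrawn for non-compliance. The documents do not say so. Section 8.5.1 makes it a deviation, deviations are summarized (Protocol 14.9, SAP 10.5), and 7.4.2 places the need for an excluded medication under stopping drug. Protocol 9.4, 9.6 and 9.7 have staff record changes in pain therapy at Day 90, follow-up and final visits, which presumes that such participants stay. This stands: the route is possible but not prescribed.

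**Drug and study withdrawal are already distinguished.** The protocol has two sections, and SAP 10.14.1 tabulates the two kinds of AE-related withdrawal separately. True, but neither document says that stopping drug leaves follow-up intact.

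**The analysis may handle it.** A reader might infer that the primary analysis is a plain observed-case comparison with no missing-data method. That cannot be concluded. SAP 7.3 states a default, much of the primary-analysis text is not visible, and MMRM is in both abbreviation lists. Such a model would use earlier VAS values, but it recovers only what those values explain.

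**The size is modest for this study.** It is a Phase 2a study with a safety primary objective and no power basis. A 3-point shift is small beside a half-width of about 14 points. This is fair and limits the weight of the point. Unresolved SAEs are also followed (Protocol 10.6), so safety follow-up does not stop altogether.

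**Conclusion.** The point holds as a gap in the follow-up rules. Applied as written, 7.4.1 and 7.4.2 can cost Day 270 VAS and later AE data for reasons plausibly tied to outcome, and the stated safeguards do not supply a Day 270 value for anyone who leaves before Day 253.

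How often this would happen, and which way it would push the result, is unknown. The shift of about 0.5 to 6 VAS points rests wholly on assumed differences in withdrawal (5 to 20 percentage points), assumed leaver–stayer gaps (10 to 30 points, equal in both arms) and an observed-case comparison. It would be smaller under a repeated-measures model, if one is specified. The documents do not support calling the Day 270 comparison biased in a known direction.

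The planned Day 180 completion of pre-v3.0 participants is a separate source of missing Day 270 values and is not counted here. The change is worth making because it is cheap and because outcomes that were never collected cannot be recovered by analysis.

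**What to change.** Leave the injection decision and the recorded list of reasons as they are. Removing lack of benefit or adverse event from the list would lose the reason-for-leaving data that a sensitivity analysis needs. Moving them into 7.4.2 would alter the grounds for stopping treatment.

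Add to Protocol 7.4.1 and 7.4.2 a statement to this effect: participants who stop study drug, start new pain therapy, have an adverse event, report lack of benefit or deviate from the protocol are asked to remain in scheduled visits (VAS, AEs, pain therapy) through their planned final visit. That visit is Day 270, or Day 180 for pre-v3.0 participants. The exceptions are withdrawal of consent, loss to follow-up, or the investigator's judgment that continued participation is not in the participant's interest.

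Extend the telephone provision in Protocol 6.2, 9 and 15.3, now limited to COVID-19 reasons, to these visits.

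**Cost.** Protocol wording, including the wider telephone provision; the visits are already scheduled. Some Day 270 values will follow new pain therapy, but that therapy is already recorded at visits and the values can be flagged.

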## 7.4.2. Early Discontinuation from Study Drug Administration

If a participant needs to discontinue study drug, the reason (i.e. due to an SAE, need for an excluded medication, etc.) should be documented in the eCRF.

NOTE: The Medical Monitor should be contacted to discuss whether to continue with planned XT-150 dosing in the event that the participant situation changes significantly in the 24 hours prior to XT-150 injection such that participant safety is at risk.

## 7.5. Replacement of Participants

After randomization, withdrawn participants will not be replaced.

## 7.6. Study Termination by Sponsor and Termination Criteria

The Sponsor reserves the right to terminate an investigational site or this clinical study at any time. Reasons for termination may include, but are not limited to, the following:

- The incidence or severity of AEs in this or other studies of XT-150 indicate a potential health hazard to participants
- Serious or persistent noncompliance by the Investigator with the protocol, clinical research agreement, or applicable regulatory guidelines in conducting the study
- IRB decision to terminate or suspend approval for the investigation or the Investigator
- Investigator request to withdraw from participation
- Participant enrollment is unsatisfactory

### 8. STUDY DRUGS

Participants will be randomly enrolled into XT-150 (150  $\mu$ g, or 450  $\mu$ g) or placebo groups and will receive two 0.5 mL intra-articular injections bilaterally (total dose of 1.0 mL) into the facet joint on Day 0 and Day 90.

